2.4.2 Secondary Endpoints

Secondary endpoints demonstrating superiority of the Calypso Knee System to HTO data for each of the following:

Recovery:

1. Time to full weight bearing

Early WOMAC Pain and Function:

2. Percent change from baseline to 3 months on the WOMAC pain in the Knee injury and Osteoarthritis Outcome Score (KOOS Knee Survey)
3. Percent change from baseline to 3 months on the WOMAC function in the Knee injury and Osteoarthritis Outcome Score (KOOS Knee Survey)

Durability of WOMAC Pain and Function:

4. Percent change from baseline to 24 months on the WOMAC pain in the Knee injury and Osteoarthritis Outcome Score (KOOS Knee Survey)
5. Percent change from baseline to 24 months on the WOMAC function in the Knee injury and Osteoarthritis Outcome Score (KOOS Knee Survey)

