Additional Observations:	
Safety Observations:
 
 • Knee Range of Motion (ROM) 
 ○ Measured passively defined as degrees of flexion and extension • Adverse Events by type, over time, severity, seriousness, and relatedness • Secondary surgical interventions by type of surgical intervention (revision, removal, re-operation (includes conversion to arthroplasty) supplemental fixation, other intervention) • Metal ion levels • In the event of a Calypso Knee System removal, the following assessments will be evaluated: 
 ○ Radiographic evaluations ○ MRI assessment as available ○ Calypso Knee System (implant) retrieval analysis ○ Histology ○ Metal Ion levels ○ Arthroplasty conversion data, if applicable 
Effectiveness/Other Observations:
 
 • Patient reported knee outcome measures and activity (KOOS Knee Survey, KSS, Subject Activity and Satisfaction, SF-12 Health Survey) • Investigator reported KSS
Statistical Analyses:	
Primary Statistical Analysis
 
The primary objective is to establish that the Calypso Knee System is non-inferior to HTO on a responder analysis combining pain, function, specified device-related SAEs, and implant integrity. A subject is considered a responder if he/she meets all success criteria that comprise the definition of the composite end-point at 24 months.
 
Secondary Statistical Analysis
 
Secondary Statistical Analysis will only be conducted upon a successful primary analysis of non-inferiority. Analysis of secondary objectives will take a hierarchical

Calyпсо Knee System Clinical Study

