2.4 Study Endpoints

2.4.1 Primary Endpoint

The primary endpoint is a 24 month composite endpoint demonstrating non-inferiority of the Calypso Knee System to HTO data. A subject is a responder if all of the following components are met at 24 months:

- Clinically significant improvement of at least 20% from baseline on the WOMAC pain questions in the KOOS Knee questionnaire with a change of ≥ 10 points
- Clinically significant improvement of at least 20% from baseline on the WOMAC function questions in the KOOS Knee questionnaire with a change of ≥ 10 points
- Freedom from the following device-related serious adverse events:
 - deep infection requiring surgical intervention (Both arms)
 - damage to adjacent neurovascular or ligament structures necessitating reconstruction (Both arms)
 - non-union (HTO only)
- Maintenance of implant integrity as evaluated by radiographic assessment

NOTE: A subject will be considered a non-responder if they have a conversion to arthroplasty or loss of implant integrity of the Calypso Knee System at 24 months

Details of the radiographic assessment for implant integrity may be found in the Radiographic Evaluation Protocol (CLIN102792).

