5.0 STATISTICAL ANALYSIS PLAN

Refer to the Statistical Considerations and Preliminary Propensity Score (PS) Design Memorandum (CLIN103113) for the Calypso Clinical Study for primary and secondary endpoint study analysis, analysis population, sample size and power, evaluation of missing data, and baseline covariates against endpoint success rates.

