5.3 Follow-Up and Reporting

All subjects enrolled and devices used in the clinical study will be accounted for in the final report. All reasons for exclusion from analysis will be carefully documented. Similarly, for all subjects and devices included in an analysis population, the measurements of all important variables must be accounted for at all relevant time points. Additional information that is available on subjects screened for entry but not enrolled will also be summarized.

Subjects with early termination will be identified and a descriptive analysis of them provided, including the reasons for their loss to follow-up and known treatment outcome.

Subjects requiring removal of the Calypso Knee System will continue to participate in follow-up through the duration of the study. These subjects will take part in all protocol required follow up examinations, test, and the completion of questionnaires.

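### Do the 24-month WOMAC durability endpoints credit Calypso with scores recorded after a knee replacement or implant removal?

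*Combined protocol and SAP*

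**What the plan says.** Section 2.4.2 groups the last two superiority endpoints under "Durability of WOMAC Pain and Function". They are "Percent change from baseline to 24 months on the WOMAC pain in the Knee injury and Osteoarthritis Outcome Score (KOOS Knee Survey") and "Percent change from baseline to 24 months on the WOMAC function in the Knee injury and Osteoarthritis Outcome Score (KOOS Knee Survey"). Each is a single line with no rule for intercurrent events.

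For the primary endpoint, Section 2.4.1 does give such a rule: "A subject will be considered a non-responder if they have a conversion to arthroplasty or loss of implant integrity of the Calypso Knee System". The rule is tied to the 24-month time point.

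Section 5.3 says of removal: "Subjects requiring removal of the Calypso Knee System will continue to participate in follow-up through the duration of the study". It adds: "These subjects will take part in all protocol required follow up examinations, test, and the completion of questionnaires". Section 2.1.1 separately asks all subjects to complete the KOOS at every follow-up visit.

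Section 5.0 does not set out the secondary analysis itself. It refers to memorandum CLIN103113 "for primary and secondary endpoint study analysis, analysis population, sample size and power, evaluation of missing data", among other matters.

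The Protocol Summary (Statistical Analyses) adds a gate: "Secondary Statistical Analysis will only be conducted upon a successful primary analysis of non-inferiority". The five secondary objectives are then tested in fixed order, each only if all those before it succeeded. The 24-month endpoints are fourth and fifth.

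**The concern.** Read together, Sections 2.4.1, 2.4.2 and 5.3 suggest a contradiction. A subject whose knee is replaced at, say, 15 months is a non-responder on the primary endpoint. If that subject then reports a good WOMAC score at 24 months and the score is used as observed, it raises the Calypso mean on an endpoint whose label refers to lasting benefit from the device. More failures could then produce a better result.

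The endpoints carry formal superiority claims, and the comparator is a cohort from an earlier non-randomized trial. If post-conversion scores were collected or handled differently in that cohort, the comparison would be distorted in a way that randomization cannot balance.

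**Working it through.** **What the documents supply.** The only usable design figure is 80 Calypso subjects. It cannot be reproduced, because the margin, alpha, power, responder rates and HTO cohort size are not in the documents. Plausible inputs for a non-inferiority comparison of two proportions give anything from 18 to 505 per arm. Event rates, post-event scores and the SD of percent change are not given either, so everything below is assumption.

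**Formulas.** Let r be the share of an arm with an event by 24 months, u the percent improvement recorded after it, and f the value under a failure rule (0%).

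- Shift in an arm's mean = r × (u − f); net shift = Calypso shift − HTO shift.
- SE = SD × √(1/80 + 1/n), with n the HTO cohort size.
- Chance of false superiority = Φ(net shift/SE − 1.96), one-sided 2.5%, with equal true means under the failure rule.

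**The unfavourable case.** Take u = 70%, n = 80 and no HTO events.

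| Calypso events | Shift | SD | SE | Chance |
|---|---|---|---|---|
| 10% | 0.10 × 70 = 7.0 | 35 | 35 × √(2/80) = 5.53 | Φ(1.265 − 1.96) = 24% |
| 5% | 0.05 × 70 = 3.5 | 35 | 5.53 | Φ(0.632 − 1.96) = 9% |
| 10% | 7.0 | 45 | 45 × √(2/80) = 7.12 | Φ(0.984 − 1.96) = 16% |
| 5% | 3.5 | 45 | 7.12 | Φ(0.492 − 1.96) = 7% |

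**Allowing events in both arms.** Take u = 60%, SD 30 to 40, n = 50 to 120.

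| Calypso / HTO events | Net shift | Chance of false superiority |
|---|---|---|
| 10% / 0% | +6.0 | 13% to 28% |
| 10% / 5% | +3.0 | 6% to 10% |
| 5% / 5% | 0 | 2.5% |
| 5% / 10% | −3.0 | 0.4% to 0.9% |

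The sign depends on which arm has more events. The documents do not say.

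**Three further checks on the premises.**

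1. Section 5.3 concerns removal, while the failure note in Section 2.4.1 names arthroplasty and loss of implant integrity. These are different events. A large u might be argued after a knee replacement, but nothing in the documents supports it after removal alone. If such a subject is no better than at baseline, u = f and the shift is nil. Whether removal counts as loss of integrity depends on the Radiographic Evaluation Protocol (CLIN102792), also not supplied.
2. The chances above apply to one endpoint tested alone. Endpoints 4 and 5 are reached only after primary non-inferiority and success on endpoints 1 to 3. Eight conversions among 80 would cost the Calypso responder rate up to 8/80 = 10 percentage points, so the scenario that inflates the durability mean also makes it less likely to be tested.
3. The calculation takes 0% improvement as the truth for these subjects. If the target is instead the outcome under a policy of starting with Calypso, whatever follows, the observed scores are the right data and there is no inflation.

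**The case for a change.** The best case for a change is that the protocol's authors saw the need for a rule in Section 2.4.1 and did not repeat it one section later. Post-event scores are observed, so a missing-data rule in CLIN103113 would not necessarily catch them. The primary gate does not remove the problem, because a non-inferiority test can pass with some conversions. Writing a rule would cost little.

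Much of this is right. The asymmetry between the two sections is real, and so is the distinction between observed and missing scores. But Section 5.0 assigns more than missing data to the memorandum. It also assigns the secondary endpoint analysis and the analysis population, which is where such a rule normally sits. Its absence from a one-line endpoint definition does not show that the plan lacks it.

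Nor does Section 5.3 say that the scores are analysed. It says that they are collected, which is good practice and is needed under any choice of estimand, including one that sets failures to zero and reports the observed scores as a sensitivity analysis.

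Setting affected subjects to no change is one of several defensible choices. Applying it after implant removal in the Calypso arm only would itself treat the arms differently, and extending it to the 3-month endpoints has no supporting analysis.

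**Conclusion.** No change to the plan is called for. The visible text leaves a detail open: how 24-month WOMAC scores after arthroplasty or removal enter endpoints 4 and 5. It names the document in which the secondary analysis is set out, and that document cannot be judged here. That the scores are credited to Calypso is an inference, not something the protocol states.

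The arithmetic of the unfavourable case is correct on its inputs, with a one-sided error of about 24% at 10% against no events (u = 70%, SD 35, 80 per arm). It needs a clear excess of events on Calypso, large improvement after them, and a failure value taken as the truth. With equal rates the bias in the difference is zero, and with more events on HTO it runs against Calypso.

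The events will not be hidden in either case. Section 5.1 reports subsequent knee surgery by type, including conversion to arthroplasty, and adds arthroplasty conversion data where a device is removed. A reader can therefore set the durability means beside the failures. This is a gap in detail that analysts working from the memorandum can fill sensibly. The conclusion would need revisiting only if CLIN103113 proved silent on post-event scores or treated the two cohorts differently.

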2.4.3 Additional Observations

Safety Observations:

- Knee Range of Motion (ROM)
 - Measured passively defined as degrees of flexion and extension
- Adverse Events by type, over time, severity, seriousness, and relatedness

Calypso Knee System Clinical Study

2.6 Study Duration

All subjects included in this study will return for follow up visits at 6 weeks, 3 months, 6 months, 12 months, 18 months and 24 months post index procedure. Evaluation of the primary endpoint will be completed on all subjects at 24 months post procedure. Follow-up visits will continue annually for a total of 5 years.

3.0 STUDY PROCEDURES

3.1 Informed Consent

[REDACTED]

3.2 Enrollment Procedure

[REDACTED]

[REDACTED]

[REDACTED]

[figure not shown]
[figure not shown]
- 

Table 3 Imaging Assessment Schedule

3.3.2 Surgical Procedure

Calypso Knee System Clinical Study

- [REDACTED]
- 3.3.3 Concomitant Procedures

[REDACTED]

- ! [REDACTED]
- ! [REDACTED]

[REDACTED]

3.3.4 Post Procedure Care (Discharge)

[REDACTED]

[REDACTED]

- [REDACTED]
- ! [REDACTED]

3.3.5 Post procedure and post-operative rehabilitation recommendations

[REDACTED]

Calypso Knee System Clinical Study

3.3.6 Post Procedure Follow Up Assessments

All subjects included in this study will return for follow up visits at 6 weeks, 3 months, 6 months, 12 months, 18 months and 24 months post index procedure and annually for 5 years post procedure.

3.3.6.1 6 week follow-up (± 14 days)

[REDACTED]

3.3.6.2 3 and 6 month Follow-Up (± 31 days)

[REDACTED]

Calypso Knee System Clinical Study

[Redacted text block]

[figure not shown]
3.3.6.3 1 year, 18 months, 2, 3, 4, and 5 Year Follow-up (\pm 60 days)

[Redacted text block]

[Redacted text block]

[Redacted text block]

Table 4 Calypso Knee System Clinical Study Schedule of Events

3.5 Termination of Subject Participation

[REDACTED]

[REDACTED]

[REDACTED]

- Subject Lost to Follow-Up: Unable to locate subject despite at least three documented attempts to notify the subject via telephone or e-mail, and by certified mail. A subject will not be considered lost to follow-up until the last scheduled follow-up visit (60 month (5 years) study time point).
- Subject Withdraw Consent: The subject requests to terminate his/her involvement in the study, therefore withdrawing his/her consent to participate in the study (the investigator must thoroughly document the reasons for termination). Attempts will be made to retrieve any follow-up data, prior to the time point at which voluntary consent was withdrawn, when available, in particular regarding possible AEs at the time of study discontinuation.
- Subject Withdrawn by Investigator: Subjects who are withdrawn by the Investigator for any reason prior to study completion.
- Subject Death: If possible, an autopsy and/or death certificate should be obtained in order to document the cause of death.

All serious device-related adverse events will be followed until resolution, stabilization or 30 days after the last subject enrolled has completed the study, whichever occurs first.

4.0 SAFETY REPORTING

[REDACTED]

4.1 Adverse Events

[REDACTED]

[REDACTED]

The Investigator, on the basis of his or her clinical judgment, will determine the relationship of the AE to the device and/or procedure based on the following categories:

1. **Unrelated:** The adverse event is determined to be solely caused by the underlying disease, disorder or condition of the subject, or attributable solely to other extraneous causes (unrelated to the device, device malfunction, or the procedure).
2. **Possibly related:** The adverse event has onset within a clinically relevant temporal relationship to exposure to the device or procedure, and is plausibly at least partially caused by or aggravated by the use of the device, device malfunction, or the procedure. It must also meet one of the following criteria: (1) follows a known or easily foreseen pattern of response to device use or procedure and (2) is not fully attributable to the underlying disease, disorder or condition of the subject, or attributable to other extraneous causes.
3. **Probably related:** The adverse event has onset within a clinically relevant temporal relationship to exposure to the device or procedure, and is more likely than not to be at least partially caused by or aggravated by the use of the device, device malfunction, or the procedure. It must also meet both of the following criteria: (1) follows a known or easily foreseen pattern of response to device use or procedure; and (2) is not fully attributable to the underlying disease, disorder or condition of the subject, or attributable to other extraneous causes. In addition, if the adverse effect is reversible upon reoperation or device exchange, and such a procedure is done, the effect disappears or lessens in severity within the expected time interval.
4. **Definitely related:** The adverse event is clearly caused by the use of the device, device malfunction, or the procedure. It must meet all following criteria: (1) has a clear temporal relationship between device exposure and onset of the event; (2) follows a known pattern of response to device use or procedure; and (3) is not reasonably attributable to the underlying disease, disorder or condition of the subject, or attributable to other extraneous causes. In addition, if the adverse effect is reversible upon reoperation or device exchange, and such a procedure is done, the effect disappears or lessens in severity within the expected time interval.

[REDACTED]

[REDACTED]

[REDACTED]

[REDACTED]

[REDACTED]

[REDACTED]

[figure not shown]
[figure not shown]
[REDACTED]

[figure not shown]
[REDACTED]

[figure not shown]

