	
approach. These analyses will be conducted sequentially, starting from the first objective with progression towards the fifth objective. Each subsequent objective is only analyzed when all of the previous analyses are successful at demonstrating superiority.
 
Additional Observations Analysis
 
Traditional confidence intervals and p-values will be reported for these analyses, as applicable.
 
 • Knee Range of Motion (ROM) – evaluation using Calypso Knee System at baseline compared to 24 months • Adverse Events by type over time, severity, seriousness, and relatedness. AEs will be tabulated and summarized as counts and percentages. AEs will also be cross-tabulated according to: 
 ○ Severity; ○ Unanticipated Adverse Device Effect (UADE) ○ Seriousness (Serious Adverse Event (SAE), Non-serious AE); ○ Device-Relatedness (Unrelated, Possibly Related, Probably Related, Definitely Related); ○ Procedure-Relatedness (Unrelated, Possibly Related, Probably Related, Definitely Related). • Secondary surgical interventions by type of surgical intervention (revision, removal, re-operation (includes conversion to arthroplasty) supplemental fixation, other intervention) • Changes in patient reported knee outcome measures and activity (KOOS Knee Survey, KSS, Subject Activity and Satisfaction, SF-12 Health Survey) as compared to baseline • Changes in Investigator reported KSS
Study Duration:	All subjects included in this study will return for follow-up visits at 6 weeks and 3, 6, 12, 18, and 24 months, then annually through 5 years.
References:	
CLIN102840: Calypso Knee System Metal Ion Protocol LBL102812: Calypso Knee System, Instructions for Use - Product Insert LBL102811: Calypso Knee System Instruments, Instructions for Use - Product Insert CLIN102845: Calypso Knee System Surgical Technique Guide CLIN102792: Calypso Clinical Study Radiographic Evaluation Protocol CLIN102799: Calypso Clinical Study Informed Consent CLIN102852: Calypso Clinical Study Implant Retrieval Protocol CLIN102838: Calypso Knee System Rehabilitation Guideline CLIN102842: Calypso Clinical Study Investigator’s Agreement CLIN103113: Statistical Considerations and Preliminary Propensity Score (PS) Design Memorandum CLIN102839: Calypso Clinical Study Surgeon Training CLIN102853: Calypso Clinical Study Monitoring Plan CLIN102859: Calypso Clinical Study CEC Charter

Calypso Knee System Clinical Study

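### Section 4.1 makes a known or foreseeable pattern a condition for the upper causality grades, so a novel device effect cannot be graded above Possibly related, however strong the evidence

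*Combined protocol and SAP*

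**What the plan says.** Section 4.1 (Adverse Events) of the combined protocol and SAP gives the rating to the site: "The Investigator, on the basis of his or her clinical judgment, will determine the relationship of the AE to the device and/or procedure". The rating is made against four listed categories.

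- *Unrelated*: "The adverse event is determined to be solely caused by the underlying disease, disorder or condition of the subject", or due solely to other extraneous causes.
- *Possibly related*: a temporal link and plausible causation, and then: "It must also meet one of the following criteria: (1) follows a known or easily foreseen pattern of response to device use or procedure and" a second criterion, that the event is not fully attributable to other causes.
- *Probably related*: a temporal link and causation more likely than not, and then: "It must also meet both of the following criteria: (1) follows a known or easily foreseen pattern of response to device use or procedure", together with the same second criterion.
- *Definitely related*: clear causation and all of three criteria, of which the second reads "2) follows a known pattern of response to device use or procedure".

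The Protocol Summary (Additional Observations Analysis) cross-tabulates adverse events by these four grades, separately for device and procedure, and also by "Unanticipated Adverse Device Effect (UADE" status. Section 5.1 plans retrieval analysis, histology and metal ion levels when an implant is removed. Section 6.3 has an independent Clinical Events Committee (CEC) adjudicate all serious adverse events.

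**The concern.** The scale merges two separate questions: whether the device caused the event, and whether an event of that kind was already recognised. In a pivotal study of an implant, harms not seen before are among the things the safety data most need to show. If recognition is a condition for the upper grades, the grade of a novel effect reflects its novelty and not the evidence. The retrieval and histology work planned for removed implants could establish causation for a new failure mode, yet the scale gives that evidence no way to raise the grade. The relatedness tables would then understate the device's role in just those events.

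**Working it through.** The plan gives no figure to reproduce, so the check is logical. The rules of section 4.1 are applied to an event with these features:

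- the temporal link is present;
- no other cause explains the event, so the second criterion of *Possibly* and *Probably* and the third of *Definitely* are met;
- the clause on reversal after reoperation or device exchange is not triggered.

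Two things vary: whether the pattern is known, easily foreseen or neither, and how *Possibly related* is read. Causation is taken as clear, the case most favourable to a high grade.

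| Pattern of the event | Possibly, if one criterion suffices | Possibly, if both are needed | Probably | Definitely | Highest grade |
|---|---|---|---|---|---|
| Known | yes | yes | yes | yes | Definitely |
| New but easily foreseen | yes | yes | yes | no | Probably |
| Neither known nor easily foreseen | yes | no | no | no | Possibly, or none |

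*Unrelated* is not available in any row, because it requires that other causes be the sole explanation.

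In the third row, *Probably* fails on its first criterion and *Definitely* on its second. Two of the three related grades are closed whichever way *Possibly* is read. Reducing the strength of causation to more likely than not, or to merely plausible, leaves the third row unchanged.

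The reversal clause does not rescue such an event. In *Probably* and *Definitely* it is a further condition, introduced by the words in addition. Improvement after removal can therefore support a grade but cannot stand in for the pattern criterion.

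For *Possibly related*, the criteria run "follows a known or easily foreseen pattern of response to device use or procedure and (2) is not fully attributable" after an opening that asks for one of them. The next two grades ask for both and for all. That one–both–all ladder makes one of two the likely intent. The conjunction still says otherwise, and on that reading the third row has no grade at all.

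**The case against.** There is a serious case that this matters little.

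- *Probably related* accepts an easily foreseen pattern. Many tissue reactions are foreseeable for this implant: Appendix A defines periprosthetic soft tissue irritation, synovitis and local adhesions. This stands, and it confines the cap at *Possibly* to effects that are neither known nor easily foreseen.
- A reader might infer that no unanticipated adverse device effect can ever be rated *Probably* or *Definitely*. The documents do not support that. No definition of the term is visible, and an event unexpected only in severity or frequency may still follow a known pattern.
- A reader might also infer that novel effects generally fall outside the scale. That depends on reading the and in *Possibly related* as requiring both criteria, which the ladder of quantifiers makes unlikely. It is a drafting ambiguity, not the plan's evident meaning.
- No visible rule acts on *Probably* or *Definitely*. Section 3.5 ties follow-up of serious events to device-relatedness without saying which grades count. The primary endpoint in section 2.4.1 uses a named list of complications. All four grades are tabulated, and unanticipated effects have their own tabulation. This stands: no effect on an endpoint is shown, and a claim that novel effects drop out of a device-related total would need a grouping of grades that the plan does not state.
- Sections 4.0, 4.1 and 6.3 are heavily redacted, and the CEC charter is a separate document. A rule for unanticipated effects could lie in any of these. This stands as a limit on confidence.

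Two answers to the objection remain. Clinical judgment does not remove the cap, because that judgment is exercised within the listed categories. CEC adjudication is stated for serious events only, and the visible text gives no different scale for it.

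**Conclusion.** The point holds for the visible text of section 4.1. A device effect that is neither known nor easily foreseen cannot be graded above *Possibly related*, whatever the proof of causation, and an effect that is new but easily foreseen cannot reach *Definitely related*. The criteria for *Possibly related* also contradict themselves.

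The size is structural: two of three related grades are closed in the first case and one in the second. How many events this would touch cannot be estimated from the documents. The effect is on the relatedness tables. The primary endpoint is little affected. The effect on follow-up of serious events depends on which grades count as device-related; if *Possibly* counts and one criterion suffices, that effect is small.

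The conclusion assumes that the redacted text and the CEC charter contain no separate rule for unanticipated effects. It is a defect of safety classification worth correcting, not a threat to the primary analysis.

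**What to change.** In section 4.1:

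1. For *Probably* and *Definitely related*, allow the pattern criterion to be met in either of two ways: by the recognised pattern as now worded for each grade or, for an event not previously identified, by other documented evidence of causation such as a mechanism, imaging, retrieval or histology findings, or improvement after removal.
2. In *Possibly related*, replace the and between the two criteria with or, so that it agrees with the instruction to meet one of them.
3. Check that the case report form guidance and the CEC charter use the same wording.

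The cost is a text change in section 4.1 and, where needed, in those two documents. No visits, tests or subjects are added. The downside is that a few more events may be rated probably or definitely related.
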